5.6.8.3 Interim Analyses and Data Monitoring

No interim analyses are planned.

Adverse events occurring during the study will be reviewed by the Study's Medical Advisory Board quarterly. If it is determined that the continuation of the investigational study presents an unreasonable risk to subjects, the study or portions of the study which present that risk will be modified to eliminate the risk or terminated. The terminated study will not be resumed without approval of the EC and any other applicable governing regulatory agencies.

5.6.8.4 Multicenter Studies

The clinical study will be conducted under a common protocol for each investigational site with the intention of pooling the data for analysis. Every effort will be made to promote consistency in study execution at each investigational site. At least half of the investigational sites and 50% of the subjects will be from the United States. The study is intended to be conducted in a manner such that a minimum of 7 subjects will be enrolled for any investigator. Investigational sites enrolling fewer than 7 subjects will be combined, within country, using the following process. The investigator with the smallest enrollment will be combined with the investigator with the largest enrollment. If there is a further need to combine data (still fewer than 7 subjects), then the data of the investigator with the second smallest enrollment will be combined, and so on. Once 7 subjects have been achieved, the process will continue to until all investigators with less than 7

subjects have been included in a group containing 7 or more subjects. The process of combining investigator data that have insufficient subjects will result in redefining the groups of investigators for the purposes of investigating pooling. These combined groups will be referred to as "analysis centers".

The consistency of treatment response will be investigated across the analysis centers subsequent to combining the data as described above. To verify that the success rate is similar among the analysis centers, an analysis will be performed to compare the results for each of the co-primary efficacy endpoints among analysis centers using a two-tailed test with α of 0.15. The MBL endpoint will be analyzed using a logistic regression. The surgical reintervention endpoint will be analyzed using Life-Table methods.

5.6.8.5 Multiple Comparisons/Multiplicity

No adjustment for multiplicity will be performed for the co-primary endpoints, since both primary endpoints are required to be met to claim overall study success.

5.6.8.6 Examination of Subgroups

The co-primary endpoints will be summarized by baseline PBAC, fibroid load and International Federation of Gynecology and Obstetrics (FIGO). Specifically, subjects will be classified based on baseline PBAC scores of 150-200, >200-300, >300-400 and >400-500. Subjects will be classified based on the largest treated fibroid, as 1 cm - 2 cm, > 2 cm - 3 cm, > 3 cm - 4 cm, > 4 cm. Subjects will also be classified based on total treatable fibroid burden, where total treatable fibroid burden will be summed across all fibroids of type 1, 2, 3, 4, 2-5 that are 1 cm or more in size. Total treatable fibroid burden will be classified as ≤ 50 cc, > 50 cc - 100 cc, > 100 cc - 150 cc, > 150 cc - 200 cc, and > 200 cc.

In addition, change in fibroid volume will be summarized for subgroups of fibroids. Fibroids will be classified based on diameter (1 cm - 2 cm, > 2 cm - 3 cm, > 3 cm - 4 cm, > 4 cm), volume (≤ 20 cc, > 20 cc - ≤ 40 cc, > 40 cc - ≤ 60 cc, > 60 cc - ≤ 80 cc, > 80 cc - ≤ 100 cc, and > 100 cc), and type.

The subgroup analyses described above are exploratory. No labeling claims will be pursued based on the results of these analyses.

5.7 Changes in the Conduct of the Study or Planned Analyses

No changes to planned analyses.

6. INDEX OF PLANNED END-OF-TEXT TABLES

Table 14.0.1.1: Summary of Subject Enrollment and Evaluability

Table 14.0.1.2: Summary of Subject Enrollment and Evaluability by Investigator

Table 14.0.2: Summary of Subjects Excluded from Analyses

Table 14.0.3: Summary of Subject Completion/Discontinuation

Table 14.1.1.1: Summary of Subject Demographic Characteristics (Full Analysis Set Subjects)

Table 14.1.1.2: Summary of Subject Demographic Characteristics (Safety Subjects)

Table 14.1.1.3: Summary of Subject Demographic Characteristics (Per-Protocol Subjects)

Table 14.1.2.1: Summary of Subject Baseline Characteristics (Full Analysis Set Subjects)

Table 14.1.2.2: Summary of Subject Baseline Characteristics (Safety Subjects)

Table 14.1.2.3: Summary of Subject Baseline Characteristics (Per-Protocol Subjects)

Table 14.2.1.1: Summary of Efficacy by Evaluation – Primary Efficacy Variables (Full Analysis Set Subjects)

Table 14.2.1.2: Summary of Efficacy by Evaluation – Primary Efficacy Variables (Per-Protocol Subjects)

Table 14.2.2.1: Summary of Efficacy by Evaluation – Secondary Efficacy Variables (Full Analysis Set Subjects)

Table 14.2.2.2: Summary of Efficacy by Evaluation – Secondary Efficacy Variables (Per-Protocol Subjects)

Table 14.2.3.1.1: Pooling Analysis of the Co-Primary Efficacy Endpoints (Full Analysis Set Subjects)

Table 14.2.3.1.2: Summary of Co-Primary Efficacy Endpoints by Analysis Center (Full Analysis Set Subjects)

Table 14.2.3.2.1: Analysis of Co-Primary Efficacy Endpoints (Full Analysis Set Subjects)

Table 14.2.3.2.2: Analysis of Co-Primary Efficacy Endpoints (Per-Protocol Subjects)

Table 14.2.3.2.3: Sensitivity Analysis of Co-Primary Efficacy Endpoints (Full Analysis Set Subjects)

Table 14.2.3.3.1: Summary of Secondary Efficacy Endpoints (Full Analysis Set Subjects)

Table 14.2.3.3.2: Summary of Secondary Efficacy Endpoints (Per-Protocol Subjects)

Table 14.2.3.4: Summary of Co-Primary Efficacy Endpoints by Subgroups (Full Analysis Set Subjects)

Table 14.2.4: Summary of Procedure Information (Full Analysis Set Subjects)

Table 14.3.1.1.1: Summary of Treatment-Emergent Adverse Events (TEAEs) that Resulted in Discontinuation from the Study (Safety Subjects)

Table 14.3.1.2.1: Summary of Treatment-Emergent Adverse Event Characteristics by Time Period (Safety Subjects)

Table 14.3.1.2.2: Summary of Subjects Reporting Treatment-Emergent Adverse Events (TEAEs) by Time Period (Safety Subjects)

CONFIDENTIAL

Table 14.3.1.2.3: Summary of Subjects Reporting Treatment-Emergent Adverse Events (TEAEs) by Severity and Time Period (Safety Subjects)

Table 14.3.1.2.4: Summary of Subjects Reporting Treatment-Emergent Adverse Events (TEAEs) by Relationship to Study Device and Time Period (Safety Subjects)

Table 14.3.1.2.5: Summary of Subjects Reporting Treatment-Emergent Adverse Events (TEAEs) by Relationship to Study Procedure and Time Period (Safety Subjects)

Table 14.3.1.3.1: Summary of Device-Related Treatment-Emergent Adverse Event Characteristics (Safety Subjects)

Table 14.3.1.3.2: Summary of Subjects Reporting Device-Related Treatment-Emergent Adverse Events (TEAEs) (Safety Subjects)

Table 14.3.1.4.1: Summary of Procedure-Related Treatment-Emergent Adverse Event Characteristics (Safety Subjects)

Table 14.3.1.4.2: Summary of Subjects Reporting Procedure-Related Treatment-Emergent Adverse Events (TEAEs) (Safety Subjects)

Table 14.3.1.5.1: Summary of Treatment-Emergent Adverse Event Characteristics by Anesthesia Type (Safety Subjects)

Table 14.3.1.5.2: Summary of Subjects Reporting Treatment-Emergent Adverse Events (TEAEs) by Anesthesia Type (Safety Subjects)

Table 14.3.1.6.1: Summary of Treatment-Emergent Serious Adverse Event Characteristics by Time Period (Safety Subjects)

Table 14.3.1.6.2: Summary of Subjects Reporting Treatment-Emergent Serious Adverse Events (TESAEs) by Time Period (Safety Subjects)

Table 14.3.1.5.1: Summary of Vital Signs – Change from Baseline (Safety Subjects)

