Subjects will be followed at 10 days, 30 days, 3 months, 6 months, 12 months, 24 months, and 36 months. The 24 and 36 month follow-up timepoints are included to gather longer-term data postmarket and will not be required to support a marketing application.

J. STUDY DURATION

Overall study duration (first subject enrolled through last subject exit) will be comprised of approximately 22 months of subject enrollment and 36 months of follow-up for a total duration of up to 58 months.

Study duration for an individual subject, once she provides her informed consent, will be up to 3 months for screening (including baseline measurements) and treatment, and 36 months for follow up for a total duration of approximately 38-39 months.

K. ENDPOINTS

Endpoints are reached at 12 months. Selected measurements will also be obtained at 10 days, 30 days, 3 months, 6 months, 24 months, and 36 months.

1) CO-PRIMARY ENDPOINTS

- (a) Reduction in menstrual blood loss (MBL) as assessed by pictorial blood loss assessment chart (PBAC)
- (b) Rate of surgical reintervention for heavy menstrual bleeding (HMB) due to treatment failure

2) SECONDARY ENDPOINTS

The following secondary endpoints will also be evaluated

- (a) Safety - adverse device effects
- (b) Reduction in total and perfused fibroid volume as measured by contrast-enhanced MRI
- (c) Change in the symptom severity score and health-related quality of life subscales of the Uterine Fibroid Symptom and Quality-of-Life (UFS-QOL) Questionnaire
- (d) Overall subject treatment outcome using the Overall Treatment Effect Scale (OTE)
- (e) Time to return to normal activity (days)
- (f) Subject Satisfaction
- (g) Change in general health outcome as measured with the EuroQOL EQ-5D questionnaire
- (h) Subject pain and tolerance of procedure
- (i) Mean institutional length of stay (LOS)
- (j) Occurrence of pregnancy and pregnancy outcome
- (k) Change in work productivity and activity impairment due to uterine fibroid symptoms as measured with the Work Productivity and Activity Impairment Questionnaire: Specific Health Problem (WPAI:SHP)

L. Selection Criteria

The criteria listed below shall be used to determine if a patient is eligible for entry into the study. A patient must meet ALL of the study inclusion criteria and NONE of the study exclusion criteria in order to be considered eligible for participation.

Inclusion Criteria

- 1) Are premenopausal
- 2) Are ≥ 25 and ≤ 50 years of age at time of enrollment

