5.5.3 Procedure Variables

Procedure information will be captured within the eCRF. The device insertion and removal times will be collected to facilitate the calculation of procedure time. Additionally, the time the subject entered the procedure room, exits the procedure room, was eligible for discharge, and was actually discharged will be collected. The procedure location will be captured (e.g. ambulatory care center, operating room, etc). The anesthesia and procedure-related medications, and number and size of each fibroid treated will also be captured, along with the number of ablations for each fibroid. In addition, an eCRF will be created to capture device malfunctions.

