5.6.1 Analysis Populations

The FAS population will be comprised of all study subjects who were treated and who do not meet any of the following criteria:

- Become pregnant during the 12-month post-procedure study period;
- Are diagnosed with a medical condition that would make assessment of menstrual bleeding invalid or unreliable.

The safety population will be comprised of subjects who were treated and have post-baseline information.

The per-protocol (PP) population will include subjects who complete 12 months of follow-up without study protocol violations. The PP population will include subjects from the FAS population who do not meet any of the following criteria:

- Violated the inclusion/exclusion criteria;
- Did not complete a 12 month PBAC;
- Are associated with protocol violations that are considered to influence the endpoint under evaluation;

Subjects who discontinue the study due to a device/procedure-related adverse event (AE) or documented lack of efficacy (without surgical reintervention) will be included in the PP population, with missing data imputed as failure for the 12-month menstrual blood loss (MBL) endpoint.

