5.6.5 Procedure Summaries

The following procedure related information will be summarized using descriptive statistics:

- Subject pain and tolerance of procedure
- Time to return to daily activities
- LOS (start of procedure to discharge)

- Time from entry into procedure room to discharge
- Procedure time
- Device malfunctions
- Procedure location (site of service)
- Number of fibroids treated
- Size of fibroids treated
- Number of ablations per fibroid
- Anesthesia and procedure-related medications
- Pain medication and narcotic use during recovery

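### Device malfunctions and procedure outcomes are tabulated only in the FAS, which drops treated women for later events; they belong in the safety population

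*SAP*

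**What the plan says.** SAP 5.6.5 lists the procedure summaries. They include "Device malfunctions" alongside pain and tolerance, length of stay, procedure time and ablations per fibroid. SAP 5.5.3 provides the data source: "an eCRF will be created to capture device malfunctions". In the SAP table index the only entry that fits these items is "Table 14.2.4: Summary of Procedure Information (Full Analysis Set Subjects"; no version on another population is listed.

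SAP 5.6.1 defines the sets. For the FAS: "The FAS population will be comprised of all study subjects who were treated and who do not meet any of the following criteria". The first criterion is "Become pregnant during the 12-month post-procedure study period"; the second is a diagnosis that makes menstrual bleeding impossible to assess reliably, with no time limit stated. The other main set has neither exclusion: "The safety population will be comprised of subjects who were treated and have post-baseline information". All the adverse-event tables in the 14.3 series carry the safety label. The per-protocol set is drawn from the FAS. None of the sets says what counts as treated.

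Pregnancy is a secondary endpoint in the protocol (Section 4 K, item "j) Occurrence of pregnancy and pregnancy outcome", and Table 2). SAP 5.6.4.2 counts six secondary endpoints and pregnancy is not one of them. SAP 5.6.6.1 mentions only that pregnancy complications will be reported, without naming a table or a set.

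**The concern.** Malfunctions, procedure time, pain at discharge and length of stay are settled on or shortly after Day 0. A pregnancy or a diagnosis months later cannot change them. Using the FAS therefore removes valid device-performance data for reasons that concern only the 12-month bleeding comparison. It also leaves one report with two denominators: safety subjects for adverse events, and FAS subjects for the malfunctions that may have caused them.

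A second gap is the undefined word *treated*. If it is read as having received an ablation, a procedure stopped by a malfunction after the device was inserted would fall outside the FAS, the safety set and the per-protocol set. Those malfunctions say most about the device.

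Third, a protocol endpoint has no planned summary. If it were placed with the existing secondary tables, such as "Table 14.2.3.3.1: Summary of Secondary Efficacy Endpoints (Full Analysis Set Subjects", the set definition would fix the first-year result in advance.

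**Working it through.** **1. Trace each outcome to its set.**

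| Outcome | Where planned | Set |
|---|---|---|
| Adverse events, including device- and procedure-related | SAP 5.6.6.1, 14.3 tables | Safety |
| Malfunctions, length of stay, pain, procedure time | SAP 5.6.5, Table 14.2.4 | FAS only |
| Six secondary efficacy endpoints | SAP 5.6.4.2, Tables 14.2.3.3.1 and 14.2.3.3.2 | FAS and PP |
| Pregnancy occurrence and outcome | Protocol 4 K and Table 2 | None stated |

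**2. Denominator.** The plan gives no malfunction, pregnancy or exclusion rate to reproduce. The only stated input is the number treated. Protocol 19.1 gives 147, which agrees with 125/(1 − 0.15) = 147.06. SAP 5.6.7 allows 125 to 150. One woman is 1/147 = 0.68 points, and between 1/150 = 0.67 and 1/125 = 0.80 points over the SAP's range, so the choice hardly matters.

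**3. Effect of one exclusion**, assuming 3 women with a malfunction among 147 (3/147 = 2.04%):
- The excluded woman had a malfunction: 2/146 = 1.37%, a fall of 0.67 points.
- She did not: 3/146 = 2.05%, a rise of 0.01 points.

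If the exclusion is unrelated to malfunction, the first case has probability 3/147, about 2%.

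**4. Chance that at least one malfunction case is lost.** With k women excluded and m with a malfunction, unrelated to each other, this is 1 − C(147−m, k)/C(147, k). All values of k and m are assumptions.
- k = 2, m = 3: 1 − (144 × 143)/(147 × 146) = 4%.
- k = 5, m = 5: 16%.
- k = 10, m = 8: 44%.

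The expected number lost is mk/147: 0.04, 0.17 and 0.54 women respectively. Under independence the expected rate does not change, because numerator and denominator shrink in proportion. A systematic bias would need exclusion to be associated with malfunction.

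**5. Pregnancy.** Assume 1 to 5 pregnancies in the first year. Among all treated women the rate is 1/147 = 0.7% (exact 95% CI 0.02% to 3.7%) to 5/147 = 3.4% (1.1% to 7.8%). The same women counted in the FAS would give 0/146 to 0/142.

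**6. Meaning of treated.** SAP 5.5.3.3 starts length of stay at device insertion, and Protocol 12.2 starts treatment time there too. Protocol 12.2, however, ends treatment time at removal following the final ablation, which has no value if none was delivered. The documents allow either reading.

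**The case against.** The strongest reply is that little is actually hidden. SAP 5.6.2 summarises reasons for exclusion from each set and for discontinuation, so pregnancies should be visible there. Adverse events are tabulated in the safety set and listed by subject. Every observed device deficiency is recorded (Protocol 14.2) and reviewed by the sponsor and the Medical Advisory Board (Protocol 14.3). A malfunction that causes an adverse event enters the device-related tables. Table 14.2.4 is descriptive, with no test or success criterion, and eligibility makes pregnancies unlikely. All of this stands, and it limits the loss to malfunctions without an adverse event and to the procedure measures of the excluded women. It does not supply a malfunction rate on the right denominator.

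Four stronger readings are tempting, and the documents do not support them.
- *Pregnancy is reported in the FAS.* It is not; it has no planned table at all.
- *Aborted procedures disappear from every table.* Enrollment precedes treatment (Protocol 10.4), so these women appear in the enrollment and disposition summaries, and their adverse events are listed. Whether they count as treated is open.
- *Each exclusion costs 0.7 points.* That holds only when the excluded woman had the event.
- *Procedure complications are what cause removal from the FAS.* SAP 5.6.1 does not say so. It keeps women who stop because of a device- or procedure-related adverse event in the per-protocol set, itself drawn from the FAS. Protocol 13.1 lists cervical stenosis and hematometrium as possible complications; whether either would count as an invalidating diagnosis is inference.

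**Conclusion.** The point holds in a limited form. Table 14.2.4 uses a set built for the bleeding endpoint to report outcomes that the exclusions have no bearing on, although the SAP already has a suitable set and uses it for adverse events. The expected effect is small: about 0.7 points when an excluded woman had a malfunction, almost nothing otherwise, and a 4% to 44% chance of losing at least one malfunction case under the assumed ranges (2 to 10 exclusions, 3 to 8 malfunctions, unrelated, 147 treated). No bias in a particular direction can be shown from the documents. The undefined meaning of treated is an ambiguity to close, not a demonstrated loss. The missing pregnancy summary is a separate and certain gap. The co-primary analyses are unaffected.

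**What to change.** 1. Run Table 14.2.4, including device malfunctions, on the safety population.
2. In SAP 5.6.1 state that, for the safety population, treated covers every woman in whom the device was inserted, whether or not an ablation was delivered. Malfunctions that stop a procedure are then counted.
3. Separately, plan a summary of pregnancy occurrence and outcome for the protocol endpoint. If a table is added, use the safety population.

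The first item costs one table header, the second one sentence, the third one new table. No new data are needed, and the sample size and the FAS definition stay as they are. The downside for the sponsor is that malfunction and procedure figures may become slightly less favourable.
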